9.3 Definitions

Adverse Event (AE) is defined as any untoward medical occurrence in a subject who was treated with an investigational product, and does not necessarily have a causal relationship with the treatment. An AE can therefore be any unfavorable and unintended sign, symptom, or disease, whether or not related to the investigational product.

Serious Adverse Event (SAE) is defined as any untoward medical occurrence that:

- results in death,
- is life-threatening,
- requires inpatient hospitalization or prolongation of existing hospitalization,
- results in persistent or significant disability/incapacity,
- is a congenital anomaly/birth defect, or
- is medically important*

* “Important medical events that may not result in death, be life-threatening, or require hospitalization may be considered a serious adverse drug experience, when based on appropriate medical judgment, they may jeopardize the subject and may require medical or surgical intervention to prevent one of the outcomes listed in this definition.” (CFR 312.32).

Expectedness: An SAE is considered “unexpected” if it is not listed in the IB or is not listed at the specificity or severity that has been observed. The Sponsor is responsible for assessing expectedness of SAE.

Suspected Unexpected Serious Adverse Event reactions (SUSAR) is defined as a SAE event occurring in a subject in an interventional study that is assessed as both causally related to the suspect product under clinical investigation and unexpected per the IB.

9.4 Relationship to Study Product

For each AE, the relationship to the study drug must be recorded as either related (there is a reasonable possibility of a causal relationship between the event and the investigational agent) or not related (there is not a reasonable possibility of a causal relationship between the event and the investigational agent). In general, a causal relationship will be assigned when facts, evidence, or arguments exist to support the causal relationship.

When assessing a relationship between investigational agent and an adverse event, the following parameters are to be considered:

- The causal relationship is reasonable on the basis of clinical judgment and given the currently available data.
- A temporal relationship exists between treatment with the investigational agent or protocol-specified procedures and the AE.
- A biologic plausibility of relationship is present.
- Any underlying concurrent illness and/or therapies the subject has received are considered.

9.5 Relationship to Study Procedure

For each AE, the relationship to the Investigational Agent delivery procedure must be recorded as either **related** (there is a reasonable possibility of a causal relationship between the event and the study procedure) or **not related** (there is not a reasonable possibility of a causal relationship between the event and the study procedure).

9.6 Severity of Adverse Events

The intensity of each event will be rated by the investigator or if needed using the following per protocol severity classifications:

Severity	Definition
Mild:	AEs are transient, require no special treatment, and do not interfere with subject's daily activities.
Moderate:	AEs introduce a low level of inconvenience or concern to the subject and may interfere with daily activities, but are usually ameliorated by simple therapeutic measures.
Severe:	AEs interrupt a subject's usual daily activities and typically require systemic drug therapy or other treatment. A severe AE is not necessarily serious; for instance, a migraine headache lasting for several hours may be considered severe but not serious. Action taken will be categorized as none, study drug discontinued, dose modified, required concomitant medication, required procedure, or other.

9.7 Procedures for Adverse Event Reporting

AE will be collected only after a subject has been randomized.

All AE (including MACCE), will be recorded by the investigator or designee as part of the study participant's medical history records and on the appropriate case report form. The investigator or designee will evaluate the relationship of the AE to both the investigational agent and study procedure as related, not related, or unknown, and will record the findings, including all pertinent details of the event on the eCRF.

The investigator will take appropriate measures to ensure the subject's well-being and document these interventions on the appropriate eCRF. The DSMB will review these events.

To maintain a consistent and thorough approach to the collection, documentation and assessment of AE, it is essential that investigators provide the Sponsor with the highest level of medical understanding of each event. This means that when describing an event, medical diagnosis is preferred to a list of symptoms. If a diagnosis can be made, which organizes or explains multiple symptoms or a cascade of events, the diagnosis will become the AE and should replace multiple symptoms in the eCRF and study records.

9.8 Protocol- Specified Serious Adverse Events

For the purposes of this study, SAE that are primary endpoint events will not be reported individually in an expedited manner. These protocol-specified SAE will be monitored by the DSMB. The DSMB will monitor the occurrence of MAACE, all-cause mortality and adverse

events of special interest (target vessel revascularization and new or worsening HF during the index hospitalization) throughout the study. The DSMB will review all safety data periodically in a blinded fashion and may request unblinding of the data, as needed. If aggregate analysis indicates that the events are occurring more frequently in the MPC treatment group this will be reported as appropriate (e.g. IND safety report, CIOMs, etc.).

The following is a list of events that will not be reported in an expedited manner:

- Death (Cardiovascular/Non-Cardiovascular/Unknown)
- Myocardial infarction
- Hospitalization for Unstable Angina
- Hospitalization for other angina/chest pain
- Hospitalization for heart failure
- Percutaneous or Surgical Coronary Revascularization
- Percutaneous or Peripheral Arterial Revascularization
- Transient Ischemic Attack
- Stroke.

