7.5.1 Un-blinding Procedure

The study blind should not be broken except in a medical emergency (where knowledge of the test material received would affect the treatment of the emergency) for regulatory requirement (e.g., suspected unexpected serious adverse reactions (SUSARs)), and for the unblinded analysis of efficacy and preliminary safety once all subjects have completed the 6-month visit. If an emergency un-blinding becomes necessary, the investigator should notify the Sponsor or Medical Monitor, as soon as possible.

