8.1 Primary Efficacy Endpoint

The primary efficacy endpoint is the change in LVESV as assessed by cardiac MRI from baseline to 6 months post investigational agent infusion for each MPC treatment group compared with control.

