9.9 Reporting Requirements

All SAE reported or observed during the trial, whether protocol defined or not and whether or not attributable to the investigational agent, must be reported to [REDACTED] within 24 hours of the knowledge of the occurrence (this refers to any AE that meets any of the aforementioned serious criteria). To report the SAE, the investigator or designee will complete the SAE form electronically in the eCRF. When the form is completed, [REDACTED] Safety personnel will be notified electronically and will retrieve the form. If the event meets serious criteria, and it is not possible to access the eCRF, the investigator or designee will send an e-mail to [REDACTED] Safety at [REDACTED] or call the [REDACTED] SAE hotline (phone number listed below) and fax the completed paper SAE form to [REDACTED] (fax number listed below) with 24 hours of awareness. When the eCRF becomes available, the SAE information must be entered within 24 hours of the system becoming available. [REDACTED] Safety personnel are available for SAE reporting on a 24-hour basis. Reports are reviewed during normal business hours of the receiving office.

Safety Contact Information:

[REDACTED] Clinical Safety

[REDACTED]

[REDACTED]

USA

[REDACTED] SAE hotline – North America/Asia Pacific:

[REDACTED]

Facsimile: [REDACTED]

e-mail: [REDACTED]

[REDACTED] SAE hotline – Europe/Israel:

Telephone: [REDACTED]

Facsimile: [REDACTED]

e-mail: [REDACTED]

The investigator must continue to follow the subject until the SAE has subsided or until the condition becomes chronic in nature, stabilizes (in the case of persistent impairment), or the subject dies. Within 24 hours of receipt of follow-up information, the investigator or designee must update the SAE form electronically in the EDC system for the study and submit any supporting documentation (e.g., subject discharge summary or autopsy reports) to [REDACTED] Safety personnel via fax or e-mail. If it is not possible to access the eCRF, refer to the procedures outlined above for initial reporting of SAEs.

The Sponsor and/or designated CRO personnel will be available to answer questions and to assist site personnel in documenting SAEs and completing the SAE eCRF.

All SAE that are considered unexpected and related to the study product will be reported by the Sponsor or its designee as a 15-day report to the Regulatory Authorities as applicable and to all participating investigators.

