SAEs that are considered unexpected, related to the study and are life threatening or result in death will be reported by the Sponsor or its designee to the regulatory authorities as applicable, and to all participating investigators as a 7-day report.

Each investigator must notify the Institutional Review Board (IRB)/ Ethics Committee (EC) responsible for reviewing the study at their site of all 15-day or 7-day safety reports required by local regulations and shall provide the Sponsor or its designee with written confirmation of said IRB/EC notification.

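### Sections 9.8 and 9.9 give opposite instructions on expedited reporting of a related and unexpected death, MI, stroke or other listed event

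*Combined protocol and SAP*

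**What the plan says.** Section 9.8 (Protocol-Specified Serious Adverse Events) says that "SAE that are primary endpoint events will not be reported individually in an expedited manner". It hands these events to the DSMB and provides for a report if aggregate analysis shows them to be more frequent under MPC. It then introduces nine bullets with "The following is a list of events that will not be reported in an expedited manner". The bullets cover death of any cause, MI, admission for unstable angina, admission for other angina or chest pain, admission for heart failure, two revascularisation lines, TIA and stroke.

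Section 9.9 (Reporting Requirements) contains three rules:

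- Site to safety desk: every SAE, "whether protocol defined or not and whether or not attributable to the investigational agent, must be reported to" the safety group within 24 hours.
- 15-day report: "All SAE that are considered unexpected and related to the study product will be reported by the Sponsor". Recipients are regulators and all participating investigators.
- 7-day report: "SAEs that are considered unexpected, related to the study and are life threatening or result in death will be reported by the Sponsor". Recipients are unchanged.

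Investigators must pass the 7-day and 15-day reports on to their IRB/EC as local regulations require.

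Two other sections bear on this. Section 9.3 defines a SUSAR as an SAE "assessed as both causally related to the suspect product under clinical investigation and unexpected per the IB". Section 7.5.1 permits breaking the blind "for regulatory requirement (e.g., suspected unexpected serious adverse reactions (SUSARs"). Neither excludes the events listed in 9.8.

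**The concern.** Take a stroke after infusion that is assessed as related to the cells and unexpected against the Investigator's Brochure. Under 9.8 it gets no individual expedited report. Under 9.9 it gets a 15-day report, or a 7-day report if it is fatal or life threatening. Safety staff working to those deadlines would find opposite answers in adjacent sections.

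Safety is part of the primary objective (section 4.1), and stroke and MI are close to the hazards that the infusion-halt guidelines in 7.1 already anticipate: an acute cerebrovascular event, ST re-elevation and unresponsive ischaemic symptoms. If 9.8 is followed, regulators and the investigators at the other sites, out of about 25, receive no individual report. The IRB/EC notifications that 9.9 attaches to those reports are then not triggered at those sites.

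**Working it through.** No sample size, rate or test is involved, so the check is a comparison of text plus a count.

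**1. The two rules side by side**

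| | Section 9.8 | Section 9.9 |
|---|---|---|
| Events covered | Nine listed categories | All SAEs that are unexpected and related |
| Limited by relatedness or expectedness? | No | Yes; that is the trigger |
| Individual expedited report by sponsor | No | Yes: 15 days, or 7 days if fatal or life threatening |
| Exception for the other section's events | None | None |
| Alternative route | Aggregate analysis showing an excess under MPC | None needed |

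The overlap is any listed event that is both related and unexpected. No sentence in 9.8 or 9.9 gives precedence, and 9.3, 7.5.1, 9.7 and 13.1 supply no exception.

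**2. Can either section simply override the other?**

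- If 9.8 prevails, every death is exempt, because its death bullet covers cardiovascular, non-cardiovascular and unknown causes. The fatal-outcome limb of the 7-day rule then has nothing to apply to.
- If 9.9 prevails, 9.8 exempts only events that 9.9 would not have expedited anyway.

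Either reading empties part of the other section, so the text does not resolve itself.

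**3. Does the stated basis fix the scope?** Section 9.8 justifies the exemption by calling these primary endpoint events. The only endpoint labelled primary is in 8.1: "The primary efficacy endpoint is the change in LVESV as assessed by cardiac MRI from baseline to 6 months". A change in ventricular volume is not an SAE. MACCE (section 4.3: cardiovascular death, non-fatal MI, non-fatal stroke, heart failure hospitalisation) does not reproduce the list either:

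- Lines matching a MACCE component: death (in part), MI, stroke, heart failure admission = 4.
- Lines matching none: unstable angina, other angina or chest pain, two revascularisation lines, TIA = 5.
- 4 + 5 = 9, all the bullets.

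Section 5.4.3 names two of those five, admission for unstable angina and TIA, as neither MACCE nor events of special interest.

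On a wider benchmark that adds all-cause mortality and the events of special interest, coronary revascularisation also matches. The split becomes 4 + 1 = 5 matching and 5 − 1 = 4 not. The list still corresponds to no defined endpoint.

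**4. Do the other safeguards fill the gap?**

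- The 24-hour rule brings the event to the safety desk, but says nothing about what the sponsor sends onward.
- The aggregate route in 9.8 needs an excess under MPC. With about 35 subjects per arm, a single case may show none.
- The scheduled DSMB reviews of MACCE come after 15, 30, 60 and 90 subjects reach Day 30, and 9.8 describes DSMB review as blinded unless unblinding is requested.
- Section 13.1 has the investigator notify the IRB/EC of any SAE. That informs the treating site's committee, not regulators or the other sites.

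**The case against.** The strongest reply is that 9.8 is a specific rule and 9.9 a general one, so the specific rule governs. Listed events would go to the DSMB and to aggregate reporting, and all other related and unexpected SAEs to 7-day or 15-day reports. Section 9.8 bars only individual reporting and names a substitute. On this view the sections are complementary, and exempting endpoint-type events is a legitimate choice. This does not hold as a reading of the text: nothing states that 9.8 prevails, exempting all deaths leaves the fatal limb of the 7-day rule empty, and the aggregate route cannot deliver a report of one case.

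Several narrower points do stand:

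- The SUSAR definition and the unblinding provision show that some SUSAR reporting is intended. They do not prove that listed events were meant to be included.
- The MACCE count bears on how the exemption is justified, not on the conflict itself, and it shifts by one line with the benchmark.
- The primary endpoint wording has a plausible source: safety is the primary objective, and 9.1 describes a primary safety analysis that includes SAE rates to 30 days.
- The practical gap is limited to sponsor reports to regulators and other investigators, and to IRB/EC notice at other sites.
- The documents do not show whether the exemption was deliberate.

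**Conclusion.** The concern holds. Sections 9.8 and 9.9 contradict each other for any listed event judged related and unexpected, and no precedence rule or exception resolves it. All nine listed categories are exposed, because the list carries no qualifier. How many events this would affect cannot be estimated: it depends on causality assessments and on what the Investigator's Brochure lists as expected, and the brochure is not among the documents. If it lists some of these events as expected, fewer cases are caught, but the contradiction remains. The effect is confined to onward expedited reporting; no endpoint, analysis or sample size changes. Because it touches the reporting of possible cell-related deaths, MIs and strokes, it should be corrected, though it does not undermine the design.

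**What to change.** - In 9.8, state that the exemption does not extend to a listed event assessed as both related and unexpected; such an event follows the 7-day or 15-day path in 9.9. This is consistent with the SUSAR unblinding provision in 7.5.1.
- In 9.9, add a matching cross-reference to 9.8.
- In 9.8, replace the reference to primary endpoint events with a reference to the events listed there, so that the scope rests on the list alone.

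If the sponsor did intend the exemption to cover related and unexpected cases, the protocol must say so, give the reason and amend 9.9, since the two sections cannot both stand.

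The cost is two or three sentences of protocol wording, with no new data, committee or analysis. The downside should be small: probably a few more expedited reports, and unblinding of those cases by the safety group. The number cannot be estimated from the documents.

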9.9 Reporting Requirements

All SAE reported or observed during the trial, whether protocol defined or not and whether or not attributable to the investigational agent, must be reported to [REDACTED] within 24 hours of the knowledge of the occurrence (this refers to any AE that meets any of the aforementioned serious criteria). To report the SAE, the investigator or designee will complete the SAE form electronically in the eCRF. When the form is completed, [REDACTED] Safety personnel will be notified electronically and will retrieve the form. If the event meets serious criteria, and it is not possible to access the eCRF, the investigator or designee will send an e-mail to [REDACTED] Safety at [REDACTED] or call the [REDACTED] SAE hotline (phone number listed below) and fax the completed paper SAE form to [REDACTED] (fax number listed below) with 24 hours of awareness. When the eCRF becomes available, the SAE information must be entered within 24 hours of the system becoming available. [REDACTED] Safety personnel are available for SAE reporting on a 24-hour basis. Reports are reviewed during normal business hours of the receiving office.

Safety Contact Information:

[REDACTED] Clinical Safety

[REDACTED]

[REDACTED]

USA

[REDACTED] SAE hotline – North America/Asia Pacific:

[REDACTED]

Facsimile: [REDACTED]

e-mail: [REDACTED]

[REDACTED] SAE hotline – Europe/Israel:

Telephone: [REDACTED]

Facsimile: [REDACTED]

e-mail: [REDACTED]

The investigator must continue to follow the subject until the SAE has subsided or until the condition becomes chronic in nature, stabilizes (in the case of persistent impairment), or the subject dies. Within 24 hours of receipt of follow-up information, the investigator or designee must update the SAE form electronically in the EDC system for the study and submit any supporting documentation (e.g., subject discharge summary or autopsy reports) to [REDACTED] Safety personnel via fax or e-mail. If it is not possible to access the eCRF, refer to the procedures outlined above for initial reporting of SAEs.

The Sponsor and/or designated CRO personnel will be available to answer questions and to assist site personnel in documenting SAEs and completing the SAE eCRF.

All SAE that are considered unexpected and related to the study product will be reported by the Sponsor or its designee as a 15-day report to the Regulatory Authorities as applicable and to all participating investigators.

SAEs that are considered unexpected, related to the study and are life threatening or result in death will be reported by the Sponsor or its designee to the regulatory authorities as applicable, and to all participating investigators as a 7-day report.

Each investigator must notify the Institutional Review Board (IRB)/ Ethics Committee (EC) responsible for reviewing the study at their site of all 15-day or 7-day safety reports required by local regulations and shall provide the Sponsor or its designee with written confirmation of said IRB/EC notification.

9.10 Pregnancy Reporting

If the subject becomes pregnant during the study, the investigator should report the pregnancy to the Sponsor, or its representative, within 24 hours of being notified. █ Safety personnel will then forward the Exposure in Utero form to the investigator for completion. The subject should be followed by the investigator until completion of the pregnancy and continue to be monitored for duration of the study. If the pregnancy ends for any reason before the anticipated date, the investigator should notify the Sponsor. At the completion of pregnancy, the investigator will document the outcome of pregnancy. If the outcome of the pregnancy meets the criteria for immediate classification as an SAE (i.e., postpartum complication, spontaneous abortion, stillbirth, neonatal death, or congenital anomaly), then the investigator should follow reporting procedures for an SAE.

10. ASSESSMENT OF FEASIBILITY

10.1 Feasibility Endpoint

Feasibility of the infusion of the investigational agent will be monitored by measurement of TIMI Flow prior to, during (approximately 50% of total investigational agent volume infused), and following the investigational agent infusion after successful PCI and stenting.

11. STATISTICAL CONSIDERATION

11.1 Introduction

The objective of this study is to determine the safety and feasibility of IC allogeneic immuno-selected, bone marrow-derived Stro3 MPC delivery in the treatment of subjects with STEMI undergoing primary PCI of the LAD coronary artery.

11.2 Statistical Methods

The primary efficacy analysis will use an ANCOVA model with baseline LVESV as covariate and alpha=0.05 to test for a difference of change in LVESV from baseline to Month 6 between each MPC arm separately and the placebo arm. If neither MPC arm is found to be better than the placebo arm and there is no difference between the MPC groups (using the ANCOVA test with alpha= 0.1) in the effect on LVESV, then the pooled MPC group will be compared to the placebo group for all functional parameters.

All other statistical tests will be considered to be exploratory (post-hoc) unless a pre-specified hypothesis exists in the statistical analysis plan (SAP), which will be finalized prior to any analysis. All statistical tests will be two-sided and statistical significance will be assessed with

respect to a nominal p-value ≤ 0.05 . Any deviations from the planned analyses will be documented and justified in the final clinical/statistical study report.

The primary efficacy analysis for LVESV will be performed using cMRI collected data. The secondary efficacy analyses for LVESV will be performed using ECHO data alone, as well as ECHO data as a substitute for missing cMRI data at baseline and/or at Month 6.

In the latter case, a regression equation will be determined between measurements for LVESV-cMRI and LVESV-ECHO over a range of values. Whenever appropriate and based on LVESV-ECHO values generated using the regression equation, a LVESV-ECHO “corrected” value will be determined and used as a replacement for missing value for LVESV-cMRI.

When all enrolled subjects have completed the study through Visit 9 (Month 6), an unblinded analysis of the safety and primary and secondary efficacy endpoints will be conducted.

The primary and secondary efficacy analyses will be performed using data collected through Visit 9 (Month 6). In addition, safety analyses will be performed on all available data through Visit 12 (Month 24) at the time of conduct of the efficacy analysis. In addition, the final safety analysis will be performed at 24 months for all patients.

No additional efficacy data will be collected beyond Visit 9 (Month 6) except for cardiac biomarkers.

